#### 12.4.4 Urinary Pharmacodynamic Parameters

The following parameters will be calculated for both Day -1 and Day 1/Day 2 in each treatment period:

- Total amount of sodium (mmol), calcium (mmol), magnesium (mmol), citrate (mmol), phosphate (mmol), cAMP (μmol) and creatinine (mmol) excreted in urine in each collection period where total amount = (total volume [L] of urine in each collection) × (concentration [mmol/L, mmol/L or μmol/L]) in pooled urine samples during a collection period
- Total amount of sodium, calcium, magnesium, citrate, cAMP and phosphate excreted in each collection period relative to the total amount of creatinine excreted in the same collection interval, mmol/mmol, nmol/mmol, or μmol/mmol
- Total amount of sodium, calcium, magnesium, citrate, phosphate, cAMP and creatinine excreted in urine over 24 hours post dose, mmol, nmol, or μmol
- Total amount of sodium, calcium, magnesium, citrate, phosphate and cAMP excreted in urine over 24 hours post dose relative to the total amount of creatinine excreted over 24 hours post dose, mmol/mmol, nmol/mmol, or μmol/mmol
- Renal clearance (CLr) of calcium, magnesium, creatinine and phosphate (mL/min) in each collection period where CLr = (Urine concentration) × (urine flow/serum concentration); urine flow is calculated as the total urine volume divided by time in the collection interval
- Fractional excretion (FE) of calcium, magnesium, and phosphate in each collection period, calculated as:

$$100 \times [\text{Urine concentration of the analyte} \times \text{Serum Creatinine}] / [\text{Serum concentration of the analyte} \times \text{Urine Creatinine}].$$

For the calculation of CLr and FE in each collection interval, the serum concentration value used is that which occurs at or closest to the middle of the urine collection period. For example, for the 0-3 hour urine collection, the serum values determined at the 1.5-hour serum sample is to be used. Calculation of these parameters will be by each time interval collected in

the CRF (0-3, 3-6, 6-9, 9-12, 12-15, 15-18, 18-24 hours for QD, and for BID this will also include 24-30, and 30-36 hours).

The following table shows the urine collection period and the corresponding timepoint to be used for the serum concentration:

Urine Collection Period	Timepoint of Collection of Serum Concentration
0-3 hours	1.5 hours
3-6 hours	4 hours
6-9 hours	8 hours
9-12 hours	10 hours
12-15 hours	13.5 hours
15-18 hours	16 hours
18-24 hours	20 hours/24 hours a
24-30 hours b	28 hours
30-36 hours b	36 hours

a 20 hours for Day 1, 24 hours for Day -1

b For BID dose groups only.

#### 12.4.5 Statistical Analysis of Pharmacodynamic Data

For serum pharmacodynamic evaluations, concentrations (raw and baseline-adjusted) of serum total calcium and albumin-corrected calcium, phosphate, creatinine, magnesium, 1,25(OH)2D3 and FGF23 will be summarized with descriptive statistics (number, arithmetic mean, SD, CV%, median, minimum, and maximum) by treatment and day. Pharmacodynamic parameters of serum total calcium and albumin-corrected calcium, phosphate, magnesium, 1,25(OH)2D3 and FGF23 will be summarized with descriptive statistics (number, arithmetic mean, SD, CV%, median, minimum, maximum, geometric mean, and geometric CV%) by treatment and day. This will be done for both raw and baseline-adjusted values, and will be done for both Day -1 and Day 1/2. Note for the Day -1 summaries, the treatment assigned will be the treatment the subject takes the following day.

Individual and mean concentration (raw and baseline-adjusted)-time plots of serum pharmacodynamic markers (serum total calcium and albumin-corrected calcium, phosphate, creatinine, magnesium, 1,25(OH)2D3 and FGF23) will be generated on both linear and semilog scales. These figures will be generated as overlay plots by treatment.

For urine pharmacodynamic evaluations, the individual urinary excretion of calcium, sodium, citrate, magnesium, cAMP, and phosphate and amount relative to creatinine of calcium, sodium, citrate, magnesium, cAMP and phosphate in each collection period as well as over 24 hours will be listed and summarized with descriptive statistics by treatment and day (Day -1 and Day 1/2).

In addition, the renal clearance of calcium, magnesium,, creatinine and phosphate and fractional excretion of calcium, magnesium and phosphate in each collection period will be summarized with descriptive statistics by treatment and day.

Individual and mean urine pharmacodynamic parameters over time (urine collection interval) will be plotted on a linear scale, overlaid by treatment (both Day -1 and Days 1 and 2 will be presented on the same plot).

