Table 3: Detailed Schedule of Assessments: Treatment Periods 1 and 2, Day 1/Day 2 (QD Regimen)																						
Study Day	1																				2	
Time point (relative to dosing time on Day 1) (h=hour/m=minute)	Pre-dose	0	10m	20m	30m	1	1.5	2	4	6	8	10	12	13	13.5	14	16	18	20	22	24	
Vital signs (blood pressure, pulse) a, b	X c					X		X	X	X	X	X	X	X		X	X	X	X	X	X	X j
ECG (12-lead) a, d	X c					X		X	X	X	X	X	X	X		X	X	X	X	X	X	X j
Randomization	X e																					
IP administration		X																				
PK blood sampling	X c		X	X	X	X	X	X	X		X		X				X					X
PD blood sampling f	X c						X		X	X	X	X	X		X		X		X			X
Anti-PTH antibody sampling g	X c																					
PD urine sampling h, i	X k	→	→	→	→	→	→	→	→	→	→	→	→	→	→	→	→	→	→	→	→	X

a An attempt to perform these assessments and procedures should be made for any subject who withdraws or is removed from the study.

b Vital signs should be collected in the supine position at each time point. Subject should also be supine at least 5 minutes prior to vitals collection. Vital signs include blood pressure and pulse.

c These assessments should be performed within 30 minutes prior to the scheduled time for IP dose administration on Day 1.

d ECGs will be performed in triplicate measurement at each time point.

e Randomization will occur prior to administration of IP of Treatment Period 1, Day 1 only (and only after all eligibility criteria have been confirmed/re-confirmed).

f PD blood sampling assessments will include: total serum calcium, magnesium, phosphate, albumin, creatinine, 1,25-dihydroxyvitamin D, and FGF23.

g The anti-PTH antibody sample should only be collected at Treatment Period 1, pre-dose (regardless of BID or QD regimen), and the sample collected within 30 mins prior to dosing.

h 24- hour urine collection for PD analysis will be collected according to the following collection intervals: 0-3 hours, 3-6 hours, 6-9 hours, 9-12 hours, 12-15 hours, 15-18 hours, 18-24 hours. ‘X’ denotes the start and stop of the entire urine collection period and ‘→’ denotes continuous collection.

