#### **12.4.2 Baseline-adjusted serum Pharmacodynamic Data**

Individual serum concentrations of pharmacodynamic markers, calcium (uncorrected and corrected for albumin), phosphate, magnesium, 1,25(OH)2D3, FGF23, and calcium-phosphate product will be baseline-adjusted at each time point. There will be two baseline definitions, one for Day -1 and one for Day 1. For Day -1, the baseline value is defined as the last non-missing value collected before the start of the active vitamin D administration on Day -1; for Day 1, the baseline value is defined as the last non-missing value collected before the administration of rhPTH(1-84) on Day 1 for each treatment period. Baseline-adjusted concentrations of pharmacodynamic markers are to be calculated by subtracting the appropriate baseline values from the raw concentrations at each time point.

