#### **12.4.3 Serum Pharmacodynamic Parameters**

Pharmacodynamic parameters will be computed from the individual raw concentrations of serum calcium (mmol/L) (uncorrected and corrected for serum albumin levels), phosphate (mmol/L), magnesium (mmol/L), 1,25(OH)2D3 (pmol/L) and FGF23 using a non-compartmental approach and actual times. pharmacodynamic parameters will be estimated for both Day -1 and Day 1 in each treatment period. Serum calcium will be corrected for serum albumin levels using the following equation:

Corrected calcium (mmol/L) = serum calcium (mmol/L) + 0.02 (40 - serum albumin (g/L))  
(Parent X1, 2009)

The following parameters will be calculated from the raw serum concentration data using WinNonlin Phoenix version 6.3 or higher (Pharsight Corporation, Mountain View, California, USA):

- AUC0-24h: the area under the concentration versus time curve, from time 0 to 24 hours
- TEmax: time to maximum effect
- Emax: maximum effect
- TEmin: time to minimum effect
- Emin: minimum effect

The same parameters will also be calculated for the calcium-phosphate product.

In addition, serum pharmacodynamic parameters will be estimated based on baseline-adjusted serum concentration of pharmacodynamic markers as follows:

- AUCabove: Area under the concentration-time curve that is above the baseline, from time 0 to 24 hours, as calculated by the linear trapezoidal method
- AUCbelow: Area under the concentration-time curve that is below the baseline, from time 0 to 24 hours, as calculated by the linear trapezoidal method
- AUCnet: AUCabove - AUCbelow
- TEmax: time to maximum effect
- Emax: maximum effect
- TEmin: time to minimum effect
- Emin: minimum effect

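### SAP 12.4.5 orders geometric statistics for baseline-adjusted serum PD parameters that are often zero or negative; a smaller gap is that 12.4.3 gives Emax, Emin and their times no time window

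*SAP*

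**What the plan says.** SAP 12.4.5 sets the summaries for the serum PD parameters of six markers (total and albumin-corrected calcium, phosphate, magnesium, 1,25(OH)2D3, FGF23). Besides number, arithmetic mean, SD and CV%, it orders "median, minimum, maximum, geometric mean, and geometric CV%) by treatment and day. This will be done for both raw and baseline-adjusted values".

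SAP 12.4.2 says the adjusted concentrations are "calculated by subtracting the appropriate baseline values from the raw concentrations at each time point". On Day 1 the baseline is the last value before rhPTH(1-84). SAP 12.4.3 then lists seven adjusted parameters: AUCabove, AUCbelow, AUCnet (the first minus the second), Emax, TEmax, Emin and TEmin. They are computed "using a non-compartmental approach and actual times". The predose sample precedes the dose: "These assessments should be performed within 30 minutes prior to the scheduled time for IP dose administration on Day 1" (footnote c to the SAP Day 1/Day 2 schedules).

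The only rule for negative adjusted values is in SAP 12.3.2, which sets negative adjusted PTH concentrations to zero. It does not extend to the PD markers.

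On the window, SAP 12.4.3 defines the raw AUC as "the area under the concentration versus time curve, from time 0 to 24 hours" and limits AUCabove and AUCbelow to the same hours. It gives Emax, Emin, TEmax and TEmin no hours. It adds that "pharmacodynamic parameters will be estimated for both Day -1 and Day 1 in each treatment period", whereas 12.4.4 says of urine: "The following parameters will be calculated for both Day -1 and Day 1/Day 2 in each treatment period". Section 12.4.5 labels the serum parameter summaries Day 1/2.

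**The concern.** A geometric mean averages logarithms, so one value at or below zero leaves it undefined. For adjusted Emin such values arise by construction; for the other adjusted parameters they arise whenever the data fall that way. The programmer must then leave the cell blank, drop the affected subjects or add a constant, and the SAP does not choose. Dropping subjects would give a geometric mean on fewer people than the arithmetic mean in the same table. The dropped people would be selected by their response.

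The raw TEmax and TEmin share the problem. When the extreme is the predose sample, the time is 0, or slightly negative if the actual draw time is kept.

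The window matters because the extremes of serum calcium describe its control, which is part of the primary objective. With BID followed to 36 h and QD to 24 h, two programmers could report different BID values from the same data.

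**Working it through.** **The plan's own count.** Protocol Table 6 gives 11 serum PD samples for QD and 15 for BID: 11 + 15 = 26, and 26 × 4 mL = 104 mL, as printed. The marked cells in the SAP schedules agree:
- QD: 0, 1.5, 4, 6, 8, 10, 12, 13.5, 16, 20, 24 h (11).
- BID: the same plus 18, 22, 28 and 36 h (15), of which 13 are at or before 24 h.

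**Sign of the adjusted parameters.** Let y0 be the baseline sample and a_i = y_i − y0, so a_0 = 0.
- Emin = min(a_i) ≤ a_0 = 0 in every profile that includes a_0.
- Emax = max(a_i) ≥ 0, and equals 0 when the baseline is the highest sample.
- AUCabove and AUCbelow are ≥ 0 and either can be 0. AUCnet can take either sign.
- The geometric mean is exp(mean of ln x), defined only for x > 0.

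**Extent of the order.** 7 parameters × 6 markers × 6 treatments × 2 days = 504 geometric means. Emin accounts for 6 × 6 × 2 = 72.

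**How often the Day 1 failure occurs for QD.** If predose is the lowest sample, then Emin = 0, AUCbelow = 0 and TEmin ≤ 0 together.

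1. Marker with no effect: P = 1/11 = 9%. At least one of 8 subjects: 1 − (10/11)^8 = 53%. At least one of 16 (Treatments B and E, cohorts combined): 1 − (10/11)^16 = 78%.
2. Calcium with the rise in protocol 2.1 (mean peak 0.125 to 0.175 mmol/L at 12 h, not back to baseline by 24 h). Assumed: linear rise and fall, 25% to 75% of the peak left at 24 h, independent sample SD 0.02 to 0.05 mmol/L; 200,000 simulated profiles per case.
   - P(predose lowest) = 0.357 to 0.774.
   - At least one of 8: 1 − (1 − 0.357)^8 = 0.971, up to 1 − (1 − 0.774)^8 > 0.9999.
   - P(AUCnet ≤ 0) = 0.000 to 0.085. At the upper end, at least one of 8: 1 − (1 − 0.085)^8 = 0.51.
   - P(adjusted Emax = 0) < 0.002.
3. Same assumptions, baseline sample left out of Emin: Emin is still ≤ 0 in 23% to 64% of profiles. At least one of 8 is affected with probability 87% to over 99.9%.
4. A separate run with SD 0.03 to 0.08 and 40% of the peak left at 24 h gives at least one of 8 with AUCbelow = 0 in 92% to 100% of summaries.

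A marker that falls after dosing mirrors this for Emax, AUCabove and TEmax.

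**Window.** Assumed: each BID dose adds 0.0625 to 0.175 mmol/L, peaking 12 h after that dose, with 50% to 75% left at 24 h and the same decline continuing; SD 0.02 to 0.05. Mean adjusted Emax over 0-36 h (15 samples) minus that over 0-24 h (13 samples) is 0.000 to 0.007 mmol/L. The upper figure is 0.007/0.125 = 6% of the lower end of the protocol's rise. TEmax falls at 28 or 36 h in 0.5% to 21% of profiles.

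**The case against.** **On the geometric statistics.** The arithmetic mean, SD, median and range are planned alongside, so no other result is lost. The minimum is shown in the same summary and Listing 5.8 gives individual adjusted parameters, so a value at or below zero could be seen. Emin fails in every profile only if the zero at baseline counts as an effect, which the SAP does not say. SAP Section 1 places table specifications in a separate document, which may hold a rule. All of this stands and limits the consequence. It does not rescue the order, because leaving the baseline sample out still gives Emin ≤ 0 in 23% to 64% of profiles under the assumptions above.

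A reader might infer that all 504 geometric means fail. They do not: only Emin fails by construction, and the others fail when the data produce a value at or below zero.

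**On the window.** The text leans towards 24 h: 12.4.3 says Day 1, the AUCs stop at 24 h, and protocol 2.1 frames the comparison over 24 hours. Against that, 12.4.5 says Day 1/2 and the synopsis rationale speaks of 24-36 hours. The Day 1/2 label does not settle it, because the QD 24 h sample also falls on Day 2. The ambiguity stands, but it is small.

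A reader might infer that BID and QD extremes are not comparable, or that BID Emin would look much worse over 36 h. The documents give no calcium course for 24 to 36 h. A late fall moves Emin appreciably only if both BID doses are assumed to have no effect.

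A reader might also infer that BID subjects go 12 h longer without supplements in Treatments A and C. SAP 2.1 withholds them until Day 2 procedures are complete. The withholding footnote to the schedule of assessments (protocol Table 1, SAP Table 2) says through the end of Day 1. These passages conflict and must be reconciled, so nothing can be built on either.

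**Conclusion.** The geometric mean and geometric CV% ordered for baseline-adjusted serum PD parameters are wrong as written. That adjusted Emin is never positive when the baseline sample is included follows from the definitions alone. The frequencies (predose lowest in about 36% to 77% of QD calcium profiles, at least one of 8 subjects affected in 97% or more of summaries) rest on the protocol's mean rise plus an assumed shape and SD. The harm is confined to these geometric statistics and to those for TEmax and TEmin. It should be corrected before the tables are programmed.

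The missing window is a minor clarification. Its effect on BID Emax is about 0 to 0.007 mmol/L under the assumed two-dose rise, and any real 24-36 h trend is not in the documents. The windowed AUCs, the 24-h urine totals and the time-point summaries are unaffected.

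**What to change.** In SAP 12.4.5, for all baseline-adjusted serum PD parameters and for TEmax and TEmin (raw or adjusted), report only the arithmetic mean and SD and the median and range already planned. Keep geometric mean and geometric CV% for raw AUC0-24h, Emax and Emin.

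In SAP 12.4.3, state that Emax, Emin, TEmax and TEmin are taken over 0-24 h for the BID-QD description, and report BID over 0-36 h separately, labelled as such. Both are needed: with a mean peak 12 h after dosing (protocol 2.1), the second BID dose is expected to peak near 24 h, the edge of the common window.

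The cost is a few sentences of SAP text and some programming on data already scheduled for collection. Nothing interpretable is given up.

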### 1.2.2 Clinical Information

Few studies of PTH use have been performed in the setting of hypoparathyroidism. Study CL1- 11-040 (REPLACE) was a double-blind, placebo controlled study of once daily (QD) administration of 50 µg to 100 µg of rhPTH(1-84) which resulted in 54.8% of the rhPTH(1-84) subjects meeting a 3-tiered primary endpoint vs 2.5% of the placebo subjects (p<0.001). Long-term, open-label studies have supported these findings with subjects maintaining the physiologic benefit derived from rhPTH(1-84) treatment. One study, PAR-C10-008 (RACE), is ongoing with some subjects receiving treatment for more than 3 years.

In clinical trials, rhPTH(1-84) significantly reduced the calcium-phosphate product. In these studies hypercalciuria was defined as an excretion of calcium in the urine greater than 300mg per 24 hours. Data from the REPLACE Study and the long-term open label study, RACE, show that rhPTH(1-84) has a calcium-sparing effect, consistent with the reduction of calcium excretion seen in a previous pharmacokinetic/pharmacodynamic study (C09-002) of single dose administration of rhPTH(1-84) in patients with hypoparathyroidism in comparison with calcitriol administration.

The Phase 3 clinical study, REPLACE, was the largest, randomized, placebo controlled clinical study conducted in hypoparathyroidism population and was the pivotal study demonstrating that rhPTH(1-84) is effective in maintaining serum calcium levels and enabling significant decreases in active vitamin D and oral calcium doses. REPLACE also established the rhPTH(1-84) dose and dose titration and evaluated the physiologic effects of PTH replacement on serum calcium, serum phosphate, urinary calcium excretion and bone turnover markers. Eighty-four subjects were evaluated in the active treatment group and 40 subjects received placebo. Subjects received at a flexible dose range of 50 to 100 µg SC in the thigh once daily for 6 months. The study met the primary efficacy triple endpoint, with a statistically higher responder rate (54.8%) versus placebo (2.5%). To meet the primary endpoint a subject had to fulfill all 3 conditions as follows: a 50% or greater reduction in oral calcium requirement, a 50% or greater reduction in active vitamin D therapy and an albumin corrected total serum calcium (ACSC) concentration that was maintained within a range of 7.5 to 10.6mg/dL.

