### 4.1 Inclusion Criteria

The subject will not be considered eligible for the study without meeting all of the criteria below.

Subjects cannot be enrolled or randomized before all inclusion criteria (including test results) are confirmed.

1. An understanding, ability, and willingness to fully comply with study procedures and restrictions.
2. Ability to voluntarily provide written, signed, and dated informed consent as applicable to participate in the study.
3. Adult men or women aged  $\geq 18$  years at the time of consent. The date of subject signature of the informed consent is defined as the beginning of the Screening Period. The Screening Period for this study may encompass both the Administrative Screening Period (if needed) and the Clinical Screening Period. For purposes of this inclusion criterion, age will only be assessed at the time the informed consent is first signed by the study subject.
4. History of hypoparathyroidism for  $\geq 12$  months, post-diagnosis, inclusive of historical biochemical evidence of hypocalcemia with concomitant serum intact PTH concentrations below the lower limit of the laboratory normal range.
5. Requirement for supplemental oral calcium treatment  $\geq 1000$  mg elemental calcium per day.
6. Requirement for therapy with active forms of vitamin D at a minimum dose of  $\geq 0.25\mu\text{g}$  per day (ie,  $\geq 0.25\mu\text{g}$  calcitriol or equivalent per day).
7. Serum calcium level within the laboratory normal reference range based on clinical chemistry lab results at the Clinical Screening Visit (based on central and/or local lab results) and Treatment Period 1, Day -2 (based on central and/or local lab results), or if outside of normal range, considered not clinically significant by the investigator.
8. Urinary calcium excretion  $\geq 200\text{mg}$  (5mmol)/24h, based on a 24-hour collection, collected anytime during the Clinical Screening Period, but prior to check-in to the CRC at Treatment Period 1, Day -2 (based on central and/or local lab results).
9. Serum magnesium level within the laboratory normal range at the Clinical Screening Visit or, if outside of normal range, considered not clinically significant by the investigator.
10. Serum thyroid function tests within normal laboratory limits at the Clinical Screening Visit, or, if outside of normal range, considered as not clinically significant by the investigator.

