#### 9.8.2 Pharmacodynamic Analysis

All pharmacodynamic analyses will be performed using the pharmacodynamic population.

Pharmacodynamic parameters will be computed from the individual concentrations of serum calcium (uncorrected and corrected for serum albumin levels), phosphate, albumin, creatinine, magnesium,  $1,25(OH)_2D_3$  and FGF23 using a non-compartmental approach. The calcium-phosphate product will be computed. Pharmacodynamic parameters will be estimated based with and without baseline adjustments.

Individual concentrations and pharmacodynamic parameters of serum total calcium and albumin-corrected calcium, phosphate, creatinine, albumin, magnesium,  $1,25(OH)_2D_3$  and FGF23 will be summarized with descriptive statistics (number, arithmetic mean, SD, CV%, median, minimum, maximum, geometric mean, and geometric CV%).

The urinary excretion of calcium, sodium, citrate, magnesium, cAMP, and phosphate will also be expressed relative to that of creatinine and will be summarized with descriptive statistics.

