## **2.5 Determination of Sample Size**

At least 8 subjects will be required to complete each treatment in each cohort. The sample size was determined based on a similar, prior pharmacokinetic/pharmacodynamic study. The number of subjects in this study is not based on statistical power considerations because the statistical analyses are primarily descriptive, and no hypothesis testing is specified in the study.

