### **3. OBJECTIVES**

#### **3.1 Primary Objectives**

To assess the pharmacokinetic profile and pharmacodynamic effects (control of serum calcium and urinary calcium excretion) of rhPTH(1-84) administered as SC doses of 25µg administered twice-daily, 50µg administered twice-daily, and 100µg administered once-daily, as well as the effect of supplemental oral calcium intake, in subjects with hypoparathyroidism.

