## 11.2 Clinical Laboratory Variables

Descriptive statistics for clinical laboratory values (in SI units) and changes from baseline at each assessment time point as well as shift tables from baseline to each visit for quantitative variables will be presented by treatment for the following clinical laboratory variables.

**Hematology** Hemoglobin, hematocrit, red blood cells (RBC), platelet count, white blood cell count – total and differential (WBC), total neutrophils, lymphocytes, monocytes, eosinophils, basophils.

**Biochemistry** Sodium, potassium, glucose, blood urea nitrogen, creatinine, calcium, chloride, thyroid stimulating hormone (TSH)a, thyroxine (T4 total)a, triiodothyronine (T3)a, 25(OH)Da, phosphorus, total protein, total CO2 (Bicarbonate), albumin, aspartate transaminase, alanine transaminase, gamma glutamyl transferase, alkaline phosphatase, total bilirubin, uric acid, Creatinine clearancea, β-HCGb, FSHb, Magnesium.

β-HCG=beta-human chorionic gonadotropin; FSH=follicle stimulating hormone; T3=triiodothyronine; TSH=thyroid stimulating hormone

a Tests done at Screening only and therefore will not appear in summary tables. They will be listed.

b Females only.

**Urinalysis** Glucose, specific gravity, blood, ketones, protein, calcium, bilirubin, pH, leukocyte esterase, and nitrites.

Clinical laboratory test values are potentially clinically important (PCI) if they meet either the low or high PCI criteria listed in Table 5. The number and percentage of subjects with post-baseline PCI values will be tabulated by treatment. The percentages will be calculated relative to the number of subjects with available baseline values and at least 1 post-baseline assessment. The numerator is the total number of subjects with at least 1 post-baseline PCI value. A supportive listing of subjects with post-baseline PCI values will be provided for all results for the parameter with a PCI value for a subject, including the subject number, site, baseline, and post-baseline values.

	Parameter	Unit	Lower Limit	Upper Limit
Chemistry	Albumin	g/L	<=20	>=90
	Alkaline Phosphatase	U/L	NA	>2*ULN
	ALT	U/L	NA	>3*ULN
	AST	U/L	NA	>3*ULN
	Bilirubin	µmol/L	NA	>2*ULN
	BUN	mmol/L	NA	>=10.7
	Chloride	mmol/L	<=80	>=125
	Creatinine	µmol/L	NA	>=177
	Glucose	mmol/L	<=1.7	>=13.9
	Gamma glutamyl transferase	U/L	NA	>=100

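### Urinary calcium, a named primary PD effect, gets no within-subject change from Day -1, and its PCI count disregards the Day -1 level

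*SAP*

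**What the plan says.** SAP 3.1 sets the primary objective, which includes "pharmacodynamic effects (control of serum calcium and urinary calcium excretion"). SAP 2.5 says that "no hypothesis testing is specified in the study", so the descriptive tables are the result.

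**Serum.** SAP 12.4.2 opens with "Individual serum concentrations of pharmacodynamic markers, calcium (uncorrected and corrected for albumin), phosphate, magnesium" and goes on to the other serum markers. Each value has the subject's own predose value for that day subtracted. SAP 12.4.3 derives parameters from the adjusted values, and the table list carries them (2.2.9-2.2.15 and 2.3.2.x).

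**Urine.** SAP 12.4.4 calculates every urine parameter for Day -1 and for Day 1/2. SAP 12.4.5 then says that the amount per interval "as well as over 24 hours will be listed and summarized with descriptive statistics by treatment and day (Day -1 and Day 1/2"). Tables 2.4.x and Figures 2.8.x and 2.9.x contain no change from Day -1.

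**PCI.** SAP 11.2 flags 24-hour urine calcium above 300 mg in men or 250 mg in women. The denominator needs only an available baseline and one post-baseline assessment. "The numerator is the total number of subjects with at least 1 post-baseline PCI value". The male limit matches the earlier trials, where "hypercalciuria was defined as an excretion of calcium in the urine greater than 300mg per 24 hours" (Protocol 1.2.2).

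**Entry.** Protocol 4.1, item 8, requires at least 200 mg (5 mmol) per 24 hours, "based on a 24-hour collection, collected anytime during the Clinical Screening Period" and before check-in on Day -2.

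**The concern.** The footnotes to Protocol Tables 2, 3 and 4 give the same seven urine intervals over 0-24 h on Day -1 and Day 1. Each subject therefore has a matched pre-dose profile in each period, but the plan does not use it to form a paired difference. Two things are lost.

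First, the spread of the change is missing for a primary outcome with about 8 subjects per cohort. The effect of oral calcium, also in the primary objective, is a comparison between cohorts because no subject enters two. Chance Day -1 differences between groups of 8 matter most there.

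Second, the only threshold measure for urine calcium cannot separate new hypercalciuria from hypercalciuria that was already present and improved. The same SAP does make this separation elsewhere. The ECG percentages use subjects with a non-PCI baseline (11.4), and the vital-sign criteria require a stated change from baseline (11.3).

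**Working it through.** The documents give no figure on this point to reproduce. The check has three parts.

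**1. Entry floor against the PCI limits** (Protocol 4.1; SAP 11.2; 40.08 mg per mmol)

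- 200 / 40.08 = 4.99 mmol, which agrees with the protocol's 5 mmol.
- 250 / 40.08 = 6.24 mmol and 300 / 40.08 = 7.49 mmol.
- 200 / 250 = 80% of the women's limit; 200 / 300 = 67% of the men's limit.

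The floor lies below both limits and applies to a screening sample. It raises the chance of a high Day -1 value without guaranteeing one.

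**2. What the PCI count can contain**

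Two invented men show the rule:

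| Day -1 | Day 1 | Change | Counted as PCI |
|---|---|---|---|
| 420 mg | 310 mg | -110 mg | yes |
| 210 mg | 310 mg | +100 mg | yes |

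How often the first pattern arises depends on a distribution that the documents do not give. Assumed: lognormal excretion, between-subject CV 35%, day-to-day CV 20% or 30%, source-population median 225 to 325 mg/24 h, and selection on a screening value of at least 200 mg. One million subjects were simulated per scenario. The simulation was re-run and the ranges were reproduced.

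- Above 300 mg on Day -1: 36-64%, i.e. 0.36 x 8 = 2.9 to 0.64 x 8 = 5.1 of 8 subjects, if all are men.
- Above 250 mg on Day -1: 55-81%, i.e. 0.55 x 8 = 4.4 to 0.81 x 8 = 6.5 of 8 subjects, if all are women.
- With an assumed 20% fall from Day -1 to Day 1, 66-94% of those counted as post-dose PCI were already above the limit on Day -1, and 42-72% of those counted had fallen.

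With source medians of 250 to 350 mg instead, 4-19% of eligible subjects are below 200 mg on Day -1.

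**3. What the separate summaries leave out**

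With complete pairs, the mean change equals the Day 1 mean minus the Day -1 mean, so the planned tables give the point estimate. They do not give its SD. If both days have the same SD and within-subject correlation r,

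SD(change) = SD x sqrt(2(1 - r)).

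At n = 8 the 95% half-width is 2.365 / sqrt(8) = 0.836 times SD(change).

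| r | SD(change) / SD | Half-width / SD |
|---|---|---|
| 0.3 | 1.18 | 0.99 |
| 0.5 | 1.00 | 0.84 |
| 0.7 | 0.77 | 0.65 |
| 0.9 | 0.45 | 0.37 |

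The summaries do not report r, so a reader of the tables could not tell which row applies.

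**The case against.** **Day -1 is not hidden.** Urine values are listed individually, summarized for Day -1 under the coming treatment, and plotted with Days 1 and 2 on the same plot. The PCI listing shows baseline for each flagged subject. This stands: a reader who works through the listings can rebuild the pairs. Only the tabulated SD of change and a cross-count are absent.

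**A protocol breach might be inferred** from Protocol 9.8.2: "Pharmacodynamic parameters will be estimated based with and without baseline adjustments". That sentence sits in the paragraph on serum concentrations, and urine has its own paragraph without such a statement. Adjusting serum only is a natural reading, so no breach is shown.

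**Worsening is captured elsewhere.** Hypercalciuria is an adverse event of special interest (SAP 11.1), and Protocol 8.1.5 judges laboratory changes by clinical relevance, shift to abnormal, or further worsening. Protocol 9.9 lists 24-hour urinary calcium among the safety data and allows for difference from baseline where applicable. SAP 11.2 names only urinalysis calcium among the variables with change and shift tables, so whether the 24-hour value receives them is unclear. The adverse event route reduces the harm from the PCI table without making that table readable.

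**The same subjects receive both regimens** within a cohort, so enrolment mix does not distort that comparison. This is correct within a cohort. The PCI table is by treatment, however, and Treatments B and E each draw on two cohorts.

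**Change from Day -1 is not a pure drug effect.** Supplements taken on Day -1 are withheld on Day 1: oral calcium and active vitamin D in Treatments A-C, active vitamin D in D-F. This stands for all six treatments and must be stated with any change table.

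**Conclusion.** The point holds as a gap in reporting. Urinary calcium excretion is one of two named primary PD effects, yet no paired change is planned and its SD cannot be had from the summary tables. The PCI count disregards baseline status, unlike the ECG and vital-sign rules in the same SAP, and has no Day -1 count beside it.

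Two stronger readings are not supported. A reader might infer that the entry criterion forces Day -1 values above the limit. It does not: the floor is 67-80% of the limits and applies at screening. A reader might also infer that the plan turns a calcium-sparing effect into an adverse signal. It does not build that in: all treatments are active, one rule applies to all, nothing is tested, and a true fall would still lower the post-dose count relative to Day -1. The risk is a misreading of one safety table.

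The structural gap follows from the text alone. Its size, 36-64% above 300 mg and 55-81% above 250 mg before dosing, rests wholly on the assumed median, CVs and lognormal shape, and is an illustration. The matter is worth settling before database lock, and it does not threaten the study.

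**What to change.** 1. In SAP 12.4.4 and 12.4.5, add for each subject and treatment the Day 1 minus Day -1 change in 0-24 h urinary calcium, as amount and as calcium/creatinine, and for each of the seven matched intervals. Summarize with n, mean, SD, median and range.
2. In SAP 11.2, keep the PCI count and set beside it a Day -1 by Day 1 cross-table for 24-hour urine calcium: new, persistent, resolved, never. Alternatively, use a non-PCI-baseline denominator as in 11.4.
3. State that 24-hour urine calcium PCI uses the 0-24 h window for both QD and BID, because BID collection runs to 36 h. State also whether the 11.2 change and shift tables include it.
4. Footnote every such table: change from Day -1 also reflects withheld supplements, namely oral calcium and active vitamin D in Treatments A-C and active vitamin D in D-F.

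The cost is SAP wording and one or two extra tables. No new samples, visits or subjects are needed.
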